7.3.3. SNOT-22 Responders

A responder is defined as a participant achieving a ≥ 8.9 -point improvement (decrease) from baseline in SNOT-22 total score at Week 52. Participants with missing data at Baseline or Week 52 (due to early study withdrawal or any other reason) will be included in the analysis as a non-responder.

7.3.3.1. Summary Measure

The summary measure of treatment effect will be the odds ratio which represents the relative odds of a participant being a responder in the mepolizumab arm compared with placebo.

7.3.3.2. Population of Interest

The population of interest is the ITT population.

7.3.3.3. Strategy for Intercurrent (Post-Randomization) Events

See Section 7.1.4. for details.

7.3.3.4. Statistical Analyses / Methods

Endpoint / Variables

 • Participants with a ≥ 8.9-point improvement from baseline in SNOT-22 score at Week 52 will be included in the analysis as a responder. • The following participants will be included in the analysis as a non-responder: 
 ○ Participants who had actual surgery prior to Week 52 ○ Participants who withdrew early from the study or who had missing data at Baseline or Week 52
Model Specification

 • See Section 7.3.1.4
Model Checking & Diagnostics

 • See Section 7.3.1.4
Model Results Presentation

 • See Section 7.3.1.4

Subgroup Analyses

- No subgroup analyses are planned for this endpoint.

Sensitivity and Supportive Analyses

- No sensitivity/supportive analyses are planned for this endpoint.

7.3.4. SNOT-22 Domain Scores

There are six proposed domain scores for the SNOT-22 (nasal, non-nasal symptoms, ear/facial symptoms, sleep, fatigue, emotional consequences). For each domain the actual and change from baseline score will be summarised by visit. These summaries will be based on datasets where the intercurrent events of actual surgery and treatment discontinuation have been handled as detailed in Section 7.1.4.

7.3.5. Need for Surgery

Participants enter the trial with severity of nasal polyps consistent with the need for surgery (inclusion criteria 8 of study protocol). Participants are identified as no longer having a need for surgery based on improvements in the total nasal polyps endoscopy score (centrally read) and overall VAS score at Week 52 (further details in Section 14.6.5). Participants with missing data at Week 52 (due to early study withdrawal or any other reason) will be identified as still having a need for surgery at Week 52.

7.3.5.1. Summary Measure

The summary measure of treatment effect will be the odds ratio which represents the relative odds of a participant no longer having a need for surgery at Week 52 in the mepolizumab arm compared with placebo.

7.3.5.2. Population of Interest

The population of interest is the ITT population.

7.3.5.3. Strategy for Intercurrent (Post-Randomization) Events

See Section 7.1.4. for details.

7.3.5.4. Statistical Analyses / Methods**Endpoint / Variables**

- Need for surgery at week 52 will be assessed for each participant as detailed in Section 14.6.5.
- The following participants will be included in the analysis as still having a need for surgery:
 - Participants who had surgery prior to Week 52
 - Participants who withdrew early from the study or who had missing data at Baseline or Week 52

Model Specification					

 A logistic regression model will be used to compare the proportion of participants who no longer have a need for surgery in the mepolizumab arm compared to placebo. The odds ratio comparing treatment groups will be estimated using the observed marginal distribution of the sample covariates. The analysis model will include the following terms: 
 
 Fixed Categorical:	Treatment group, Region	
 
 Fixed Continuous:	Baseline total nasal polyps endoscopic score (centrally read data), Baseline overall VAS score, Log_e baseline blood eosinophil count	
 
 
 Participants with missing covariate information will be excluded from the analysis 		Fixed Categorical:	Treatment group, Region	Fixed Continuous:	Baseline total nasal polyps endoscopic score (centrally read data), Baseline overall VAS score, Log _e baseline blood eosinophil count
Fixed Categorical:	Treatment group, Region				
Fixed Continuous:	Baseline total nasal polyps endoscopic score (centrally read data), Baseline overall VAS score, Log _e baseline blood eosinophil count				
Model Checking & Diagnostics					

 Models will be checking for issues with convergence. 					
Model Results Presentation					

 The number and percentage of participants identified as no longer having a need/still having a need for surgery will be displayed by treatment group, the still having a need for surgery group will be further categorized to display the number participants with actual surgery, the number withdrawn early from the study and the number with missing Baseline data. The estimated odds ratio, 95% CI and p-value comparing treatments from the logistic regression model will be displayed. 					
Subgroup Analyses					

 No subgroup analyses are planned for this endpoint. 					
Sensitivity and Supportive Analyses					

 No sensitivity/supportive analyses are planned for this endpoint. 					

7.3.6. Rate of Nasal Surgery

A summary of the number and percentage of participants who have undergone surgery will be presented, the rate of surgery will also be presented for each treatment arm.

7.3.7. Time to First Inclusion on Waiting List for NP Surgery

A summary and graph of the Kaplan-Meier estimates of the cumulative proportion of participants having been placed on a waiting list for nasal polyps surgery/sinuplasty over time will be provided.

7.3.8. Waiting List for NP surgery

A summary of the number and percentage of participants placed on a waiting list for nasal polyp surgery at each visit and over the whole study will be presented.

7.3.9. Change from baseline in UPSIT (University of Pennsylvania Smell Identification Test)

UPSIT is designed to test the function of an individual's olfactory system. The test is scored out of 40 with a lower score indicating a worse outcome. The test will be performed only by participants at sites in the UK, US and Canada. Details regarding the summary measure, population of interest and the strategy for intercurrent events are provided in Section 7.1.2 to Section 7.1.4.

7.3.9.1. Statistical Analyses / Methods

Endpoint / Variables					

 Change from baseline in UPSIT at Week 52 					
Model Specification					

 The p-value for the difference in median change from baseline between treatments will be based on the non-parametric Wilcoxon rank-sum test. The difference in median change from baseline with 95% confidence intervals will be estimated by quantile regression using a bootstrap approach. The analysis model will include the following terms: 
 
 Fixed Categorical:	Treatment group, Country	
 
 Fixed Continuous:	Baseline score, Log_e baseline blood eosinophil count	
 
 		Fixed Categorical:	Treatment group, Country	Fixed Continuous:	Baseline score, Log _e baseline blood eosinophil count
Fixed Categorical:	Treatment group, Country				
Fixed Continuous:	Baseline score, Log _e baseline blood eosinophil count				
Model Checking & Diagnostics					

 Models will be checked for issues with convergence. 					
Model Results Presentation					

 Median change from baseline within each treatment group. Estimated difference between treatments in median change from baseline with 95% confidence interval (CI) and p-value comparing treatments from the Wilcoxon rank-sum test. 					
Subgroup Analyses					

 No subgroup analyses are planned for this endpoint. 					
Sensitivity and Supportive Analyses					

 No sensitivity/supportive analyses are planned for this endpoint. 					

7.3.10. Change from baseline in PnIF (Peak Nasal Inspiratory Flow)

A PnIF meter will be used to derive forced inspiratory peak flow through the nose. A summary of PnIF data and change from baseline at each visit will be presented. These summaries will be based on a dataset where the intercurrent events of surgery/sinuplasty and treatment discontinuation have been handled as detailed in Section 7.1.4.

7.3.11. Health Outcomes

7.3.11.1. SF-36 Mental Component Summary (MCS), Physical Component Summary (PCS) and 8 summary scores

Certified scoring of the SF-36 survey will be performed using OPTUM™ software.

The eight domain scores (bodily pain, general health, mental health, physical functioning, role emotional, role physical, social functioning and vitality) as well as the physical and mental component summary scores are provided by the software.

Domain and component summary scores will be summarised by visit, including change from baseline. These summaries will be based on a dataset where the intercurrent events of surgery/sinuplasty and treatment discontinuation have been handled as detailed in Section [7.1.4](#).

7.3.11.2. Work Productivity and Activity Impairment Questionnaire (WPAI)

The WPAI questionnaire is an instrument to measure impairment in paid and unpaid work. Summary information from the WPAI at each visit will include information on employment status, hours missed from work due to health problems and due to other reasons, hours actually worked, and how much health problems affected productivity and activity.

7.3.12. Systemic Steroid Use

7.3.12.1. Number of mgs per year of prednisolone-equivalent OCS dose for nasal polyps up to Week 52

The total number of milligrams (mgs) of prednisolone-equivalent OCS per year for nasal polyps will be summarised for each treatment arm based on the use reported for each subject up to Week 52, data will be included in the summary regardless of the occurrence of events such as surgery or treatment discontinuation.

7.3.12.2. Days on Therapy

The mean number of days and percentage of days on systemic steroids for nasal polyps will be presented for each treatment arm. Data will be included in the summary regardless of the occurrence of events such as surgery or treatment discontinuation.

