
 
To further evaluate the efficacy of 100mg mepolizumab compared to placebo on systemic steroid use such as OCS and antibiotic use as part of SoC
 
	
 
Number of Courses of systemic steroid therapy up to Week 52.
 
Number of mgs per year of prednisolone-equivalent OCS dose up to Week 52.
 
Number of days on systemic steroid therapy up to Week 52.
 
Time to first course of OCS up to Week 52.
 
Number of courses of antibiotic up to Week 52.
 

 
To further evaluate the efficacy of 100mg mepolizumab compared placebo in the sub-group of participants with Asthma
 
	
In addition to endoscopic NP score, VAS symptoms score, medication and surgery, the following asthma related endpoints will be assessed:
 
 
Change from baseline in Asthma Control Questionnaire (ACQ - 5) score at Week 52.
 
Number of clinically significant asthma exacerbations defined as worsening of asthma requiring systemic corticosteroids (i.v. or oral steroid) for at least 3 days or a single IM CS dose and/or ED visit and/or hospitalisation for asthma up to Week 52.
 

 
To assess the maintenance of response after cessation of mepolizumab treatment compared to placebo
 
	
For all participants who enter post treatment follow-up period, the following will be assessed at Week 76:
 
 
Change from baseline in total endoscopic NP score.
 
Change from baseline in mean nasal obstruction VAS score.
 
Change from baseline in mean individual VAS symptom score for nasal discharge, mucus in throat, loss of smell, facial pain and overall VAS symptom score during the 4 weeks prior to Week 76.
 
Number of mgs per year of prednisolone-equivalent OCS dose.
 
Change from baseline in SNOT-22 total score.
 
Change from baseline in SF-36 Mental Component Summary (MCS), Physical Component Summary (PCS) and 8 summary scores.
 
Change from baseline in WPAI Questionnaire.
 
Time to first nasal surgery including off treatment period from randomization to Week 76.
 
Time to first inclusion on waiting list for NP surgery up to Week 76.
 

Objectives	Endpoints
Safety	

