Two Phase II studies conducted with mepolizumab in severe NP suggest that although treatment with up to 6, 4-weekly doses, are sufficient to demonstrate efficacy of mepolizumab compared to placebo, the maximal effect may not have been achieved. Extending the exploration to thirteen 4 weekly doses will therefore increase the knowledge on the time to potential maximal effect.

In Study CRT110178 significant clinical improvement in NP score was observed after two doses of mepolizumab. The second study, MPP111782, also demonstrated a reduction in the need for surgery, as assessed by a pre-defined composite endpoint based on endoscopic NP score and overall VAS symptom score after 6 doses. A reduction in the number of participants undergoing surgery was also observed. Surgery is an important endpoint for patients and physicians as well as payors as it shows a direct cost burden. Given there is a potential for delay between the decision to have surgery and the actual surgical event, this study will also measure time to admission to a waiting list for NP surgery, a potential surrogate for actual surgery.

Short courses of OCS are part of SoC for severe NP and are known to provide significant improvements in symptoms and reduction in NP size. However, this form of treatment strategy is limited by the short-lived beneficial effects and the significant systemic adverse events, which prevent prolonged and/or frequent use. If mepolizumab is

effective, it has the potential to reduce the overall exposure of patients to systemic steroid therapy, and this will be measured in the study.

The target population for mepolizumab in NP is patients who are refractory to current SoC and highly symptomatic as a consequence. Mepolizumab is intended to be administered chronically on a background of INCS, and other medical therapy usually given as short courses as required (OCS, occasional nasal douching, antibiotic courses) before surgery is considered. There is currently no other chronic treatment that can be added to INCS that can be considered appropriate for an active control in this population. As such, placebo added to SoC will be utilized as the appropriate control.

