
 • To further evaluate the efficacy of 100mg mepolizumab compared to placebo on systemic steroid use such as OCS and antibiotic use as part of SoC 	
 • Number of Courses of systemic steroid therapy up to Week 52. • Number of mgs per year of prednisolone-equivalent OCS dose up to Week 52. • Number of days on systemic steroid therapy up to Week 52. • Time to first course of OCS up to Week 52. • Number of courses of antibiotics up to Week 52.

 • To further evaluate the efficacy of 100mg mepolizumab compared to placebo in the subgroup of participants with Asthma 	
In addition to endoscopic NP score, VAS symptoms score, medication and surgery, the following asthma related endpoints will be assessed:
 
 • Change from baseline in Asthma Control Questionnaire (ACQ-5) score at Week 52. • Number of clinically significant asthma exacerbations defined as worsening of asthma requiring systemic corticosteroids (i.v. or oral steroid) for at least 3 days or a single IM CS dose and/or ED visit and/or hospitalisation for asthma up to Week 52.

 • To assess the maintenance of response after cessation of mepolizumab treatment compared to placebo 	
For all participants who enter post treatment follow-up period, the following will be assessed at Week 76:
 
 • Change from baseline in total endoscopic NP score (centrally read data). • Change from baseline in mean nasal obstruction VAS score. • Change from baseline in mean individual VAS symptom score for nasal discharge, mucus in throat, loss of smell, facial pain and overall VAS symptom score during the 4 weeks prior to Week 76. • Number of mgs per year of prednisolone-equivalent OCS dose. • Change from baseline in SNOT-22 total score. • Change from baseline in SF-36 Mental Component Summary (MCS), Physical Component Summary (PCS) and 8 summary scores. • Change from baseline in WPAI Questionnaire.

CONFIDENTIAL

2020N427698_00

205687

Objectives	Endpoints
	
 • Time to first nasal surgery including off treatment period from randomization to Week 76. • Time to first inclusion on waiting list for NP surgery up to Week 76.
Safety Objectives	Safety Endpoints

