7.3.12.3. Time to First Course of Systemic Steroids

A summary and graph of the Kaplan-Meier estimates of the cumulative proportion of participants with a first course of systemic steroids for nasal polyps over time will be provided.

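### The SAP limits its planned summaries of steroid burden to nasal-polyp use, although the protocol, SAP 2.1 and SAP 14.6.5 set no indication limit and the change is not declared

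*SAP*

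**What the plan says.** Protocol 5.4 explains why steroid use is studied. If mepolizumab works, "it has the potential to reduce the overall exposure of patients to systemic steroid therapy, and this will be measured in the study". Protocol Section 4 then lists, among the other endpoints, the number of courses of systemic steroid therapy, "Number of mgs per year of prednisolone-equivalent OCS dose up to Week 52", days on systemic steroids, and "Time to first course of OCS up to Week 52". None of these names an indication. SAP 2.1 repeats the list, for example "Number of days on systemic steroid therapy up to Week 52". The secondary endpoint, the proportion needing systemic steroids, does name nasal polyps in both documents.

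The analysis text in the SAP is narrower. Section 7.3.12.1 says "The total number of milligrams (mgs) of prednisolone-equivalent OCS per year for nasal polyps will be summarised for each treatment arm". Section 7.3.12.2 says "The mean number of days and percentage of days on systemic steroids for nasal polyps will be presented for each treatment arm". Section 7.3.12.3 plans Kaplan-Meier estimates of the proportion of "participants with a first course of systemic steroids for nasal polyps over time will be provided". Tables 2.52, 2.53 and 2.54 carry the same limit in their titles, as does Table 2.68 for the follow-up subset.

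**The concern.** Someone following SAP 7.3.12 will report a narrower quantity than the endpoint that the protocol and SAP 2.1 define. Someone following the derivations in SAP 14.6.5 will report the wider one. The plan should not leave that choice to the programmer.

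The difference matters most for participants with asthma. They are enrolled, and three days of systemic steroid or a single intramuscular dose for worsening asthma is one way to meet the definition of a clinically significant exacerbation (protocol Section 4). Under 7.3.12, a participant whose only steroid courses were for asthma contributes 0 mg and 0 days. The steroid analysis by asthma status (SAP 7.4, Table 2.34) is also limited to nasal polyps, so it does not fill the gap.

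**Working it through.** The plan gives no figure to reproduce, so the check is a comparison of text.

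| Quantity | Protocol 4 and SAP 2.1 | SAP analysis text and displays | SAP 14.6.5 |
|---|---|---|---|
| Number of courses to Week 52 | no limit | shown only with the nasal-polyp proportion (7.2.4.4, Table 2.33; by asthma status in Table 2.34) | no indication filter |
| mg/year | no limit | nasal polyps (7.3.12.1, Table 2.52) | filtered by route only (oral, IV, IM) |
| Days on therapy | no limit | nasal polyps (7.3.12.2, Table 2.53) | sum over all the participant's courses |
| Time to first course | no limit | nasal polyps (7.3.12.3, Table 2.54); no limit in the title of Figure 2.19 | no separate derivation |
| mg/year, follow-up subset | no limit | no limit in 7.5; nasal polyps in Table 2.68 | as for mg/year |

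**Is the change declared?** Table 1 of SAP 2.4 lists one departure from the protocol, the use of centrally read NP scores. The SAP 1.1 revision log says only that Section 7 and 14.6.5 were revised to reflect protocol Amendment 4. That amendment moved mg/year from secondary to other and added no indication limit.

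**Does another display restore the total?**
- Table 1.20 summarises systemic corticosteroids started between first dose and last dose plus 28 days. It is a concomitant-medication table with no mg, days or time to first course specified. Its shell is not in the SAP, so its exact content cannot be confirmed.
- Table 2.62 counts asthma exacerbations, not steroid.
- Table 2.67 counts courses with no limit in its title, but only for the follow-up subset.
- Listing 13 gives individual medication entries, not totals.

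No planned Week 52 summary is therefore specified to give mg/year, days or time to first course for any indication.

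**What the two readings do to one participant (assumed values).** Take one 10-day course for nasal polyps and one separate 7-day course for asthma over 365 days.
- SAP 14.6.5: 10 + 7 = 17 days; 100 × 17/365 = 4.7%.
- SAP 7.3.12.2: 10 days; 100 × 10/365 = 2.7%.

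**What share of exposure is captured.** If a fraction s of steroid days is for other indications, the nasal-polyp summary captures 1 − s. For assumed s of 0, 0.2 and 0.4 this is 100%, 80% and 60%. The documents do not give s.

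**Effect on the arm difference.** The all-indication difference is D(all) = D(nasal polyps) + D(other). The SAP reports only D(nasal polyps), so the gap is D(other). It is zero if steroid use for other indications is equal in the two arms, and takes the sign of the imbalance otherwise. Nothing in the documents fixes D(other).

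**The case against.** The strongest defence is that the narrower reading was intended. The objective concerns efficacy "on systemic steroid use such as OCS and antibiotic use as part of SoC". Protocol 5.1 describes the study's standard of care as care for nasal polyps, including short OCS courses, and 9.2.4 ties the OCS dose to the participant's nasal-polyp condition. The paragraph in 5.4 also opens with OCS courses for severe nasal polyps. Amendment 4, after regulatory feedback, turned the secondary endpoint from total burden to need for steroids for nasal polyps. On this view SAP 7.3.12 only makes the objective explicit.

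This reading is arguable but not settled. Protocol 7.6 uses the same term for baseline asthma treatment. Antibiotics fall under the same objective, yet SAP 7.3.13 counts them without an indication limit. The authors wrote the nasal-polyp limit into the proportion endpoint and left it out of the others, and SAP 14.6.5 does not adopt it. If the limit is intended, it still has to be declared and the sections made to agree.

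A reader might go further and infer that the trial no longer measures overall steroid exposure. The documents do not support that: protocol 7.6 requires every medication to be recorded with reason, dates and dose, and 9.2.4 requires the dose and duration of steroid courses. Only the planned summaries are narrowed.

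A reader might also infer that the reported arm difference is biased, perhaps in the sponsor's favour. Protocol 3.2.3 reports fewer exacerbations and less OCS use in the asthma programme. If that carried over here, leaving out asthma courses would understate the benefit of mepolizumab. That is extrapolation from another population, and an average omitted dose built from an assumed asthma share, exacerbation rate and dose per course would not be a between-arm difference.

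**Conclusion.** The point holds as an undeclared narrowing of planned summaries, together with a contradiction inside the SAP: 2.1, 7.5, 14.6.5 and Figure 2.19 on one side, 7.3.12 and Tables 2.52-2.54 and 2.68 on the other. Steroid given for asthma exacerbations is left out of the burden that 7.3.12 would report. How much is left out, and whether it differs between arms, cannot be derived from the documents; the percentages above rest on assumed shares.

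Severity is low to moderate. These are descriptive other endpoints. They sit outside the testing hierarchy and do not enter the sample size, so type I error, power and the confirmatory claims are unaffected.

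**What to change.** - Report number of courses, mg/year, days on therapy and time to first course for systemic steroids given for any indication, with the nasal-polyp-only version beside each.
- Make SAP 2.1, 7.3.12, 7.5, 14.6.5, Tables 2.52-2.54 and 2.68, and Figure 2.19 agree. In the same edit, settle whether time to first course counts OCS, as in the endpoint lists, or all systemic steroids, as in 7.3.12.3.
- List any restriction that remains, with its reason, in Table 1 of SAP 2.4.
- Leave the tested endpoint, the proportion requiring systemic steroids for nasal polyps, unchanged.

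The cost is SAP wording and a repeat of existing tables without the indication filter. No new data are needed, because reason for use, dose and dates are already recorded.
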